17.1 Variables and derivations

The following vital signs will be reported for this study:

- Weight (in Kgs)
- Diastolic Blood Pressure (mmHg)
- Systolic Blood Pressure (mmHg)
- Pulse (beats per minute)
- Temperature

17.2 Analysis

Population: SAF and PP

Stratification: Table: Add the strata as needed in case subjects with dose modification exceeding 20% based on enrolled population as per section 7.3:

- a. Subjects on 1.5 mg only
- b. Subjects on 0.75 mg only
- c. Subjects with any dose modification*

* Subjects who have received at least one dose of 1.5 mg and at least one dose of 0.75 mg

Listing: by subject, visit and each vital sign parameter

Statistics: The vital signs except temperature will be summarised as actual and change from baseline (number of patients, mean, SD, median, minimum, maximum, and interquartile ranges) for table. The listing will be presented for all vital sign parameters. Mean \pm SD plot will be provided for Vital sign parameters.

18. Primary endpoint**18.1 Incidence of AEs (deaths, SAEs, TEAEs, and hypoglycemia, including severe hypoglycemia)****18.1.1 Variables and derivations**

Variables:

- All AEs will be captured in the “Adverse Events” eCRF form.
- Hypoglycemia events will be captured in the “Hypoglycemic events” eCRF form.

Derivations:

- To identify incidence of deaths the eCRF question “the severity of the adverse event” = “Death” will be used from AE form.
- If the question “the adverse event serious” is indicated as “Yes” then corresponding events will be considered as SAEs.
- If the AE started on or after the first treatment administration date will be considered as TEAEs.
- Hypoglycemia events will be captured and identified using the “Hypoglycemic events” eCRF form.
- If the question “Did subject have any Hypoglycemic events” is “Yes” on “Hypoglycemic events” eCRF form and the question “the adverse event serious” is indicated as “Yes” on the AE eCRF form, then corresponding events will be considered as severe hypoglycemia events.
- The incidence of AEs= Number of new AEs post intervention/Total eligible population *100.
- The incidence of hypoglycemic AEs= (Number of new hypoglycemic AEs post intervention/Total eligible population)*100.
- Number of hypoglycemic events per patient-year (365.25 days)= Number of patients with hypoglycemic events /365.25
- Exposure Adjusted AE Incidence= Number of patients with new or worsened AEs during treatment period / (Patient-year exposure/365.25)
- Patient-year exposure is counted in days up to the AE (or end of time at risk for subjects without AE).

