8.3.5. Hypoglycemia

Participants will be trained by authorized study personnel about signs and symptoms of hypoglycemia and how to treat it. Hypoglycemia events entered into the participant paper diary will be reviewed by investigators at site visits or over telephone.

Hypoglycemia classification and definitions

Level 1

Glucose <70 mg/dL and ≥ 54 mg/dL

Level 1 hypoglycemia can alert a person to take action such as treatment with fast-acting carbohydrates. Providers should continue to counsel participants to treat hypoglycemia at this glucose alert value.

Level 2

Glucose <54 mg/dL

Level 2 hypoglycemia is also referred to as documented or BG confirmed hypoglycemia. The glucose threshold is clinically relevant regardless of the presence or absence of symptoms of hypoglycemia.

Level 3

Severe hypoglycemia

A severe hypoglycemic event is characterized by altered mental or physical status requiring assistance of another person to actively administer carbohydrate, glucagon, or other resuscitative actions for its treatment.

The determination of an episode of severe hypoglycemia is made by the investigator based on the medical need of the participant to have required assistance and is not predicated on the report of a participant simply having received assistance.

Examples of severe hypoglycemia in adults are

- altered mental status and the inability to assist in their own care
- semiconscious or unconscious, or
- coma with or without seizures.

Glucose measurements may not be available during such an event, but neurological recovery attributable to the restoration of glucose concentration to normal is considered sufficient evidence that the event was induced by a low glucose concentration.

Nocturnal hypoglycemia

Nocturnal hypoglycemia is a hypoglycemia event, including severe hypoglycemia, that **occurs at night** and presumably during sleep between midnight and 0600 (6:00 am).

Reporting of severe hypoglycemic events

If a hypoglycemic event meets the criterion of severe, the investigator must record the event as serious on the SAE paper form and report it to Lilly as an SAE.

The investigator should also determine if repeated or prolonged episodes of hypoglycemia occurred prior to the severe event.

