10.3.2. Definition of SAE

An SAE is defined as any untoward medical occurrence that, at any dose, meets 1 or more of the criteria listed:

a. Results in death**b. Is life threatening**

The term *life threatening* in the definition of *serious* refers to an event in which the participant was at risk of death at the time of the event. It does not refer to an event, which hypothetically might have caused death, if it were more severe.

c. Requires inpatient hospitalization or prolongation of existing hospitalization

- In general, hospitalization signifies that the participant has been admitted to the hospital or emergency ward (usually involving at least an overnight stay) for observation and/or treatment that would not have been appropriate in the physician's office or outpatient setting. Complications that occur during hospitalization are AEs. If a complication prolongs hospitalization or fulfills any other serious criteria, the event is serious. When in doubt as to whether hospitalization occurred or was necessary, the AE should be considered serious.
- Hospitalization for elective treatment of a preexisting condition that did not worsen from baseline is not considered an AE.

d. Results in persistent disability/incapacity

- The term disability means a substantial disruption of a person's ability to conduct normal life functions.
- This definition is not intended to include experiences of relatively minor medical significance such as uncomplicated headache, nausea, vomiting, diarrhea, influenza,

and accidental trauma (for example, sprained ankle), which may interfere with or prevent everyday life functions but do not constitute a substantial disruption.

e. Is a congenital anomaly/birth defect
 
• Abnormal pregnancy outcomes (for example, spontaneous abortion, fetal death, stillbirth, congenital anomalies, and ectopic pregnancy) are considered SAEs.

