14.2 Analysis

Population: SAF and PP

Stratification: Table: Add the strata as needed in case subjects with dose modification exceeding 20% based on enrolled population as per section 7.3:

a. Subjects on 1.5 mg only by ATC and PT

b. Subjects on 0.75 mg only by ATC and PT

c. Subjects with any dose modification* by ATC and PT

* Subjects who have received at least one dose of 1.5 mg and at least one dose of 0.75 mg

Listing: By subject

Statistics: Prior and concomitant medication will be summarized separately as (frequency, percentages) for table and listing will be presented.

15. Adverse events**15.1 Variables and derivations**

Adverse Events (AEs) will be coded using MedDRA central coding dictionary, Version (refer to DMP for dictionary version).

For the definition of Adverse events (AE) and Serious adverse event (SAE) refer to the protocol section 10.3.

TEAEs are defined as events that are newly reported after the first study drug treatment or are reported to have worsened in severity after the first study drug treatment.

In section 24 Appendix 2 the algorithm is given for calculation of partial date imputation for adverse events (AEs), and it will be used for partially missing adverse event start and end date imputation.

The following parameters will be summarised for the overview of participants' adverse events:

- Any AEs
- Any TEAEs
- Related TEAEs
- Severity of TEAEs (Mild, Moderate, Severe, Life threatening and Death)
- Outcome of AEs (Recovered or resolved, Recovering, or resolving, Not recovered or not resolved, Recovered, or resolved with sequelae, Fatal and Unknown)
- Serious AEs
- AEs leading to Discontinuation from the study
- AEs leading to Death
- Related AEs leading to Death

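### SAP 18.1.1 infers severe hypoglycaemia from the serious flag and derives TEAEs from start date alone, so two primary-endpoint counts depart from the protocol definitions

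*SAP*

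**What the plan says.** **Severe hypoglycaemia.** SAP 18.1.1 combines two form fields. The first is the hypoglycaemia form question "Did subject have any Hypoglycemic events". The second is the serious question on the adverse event form. If both are yes "on the AE eCRF form, then corresponding events will be considered as severe hypoglycemia events". Protocol 8.3.5 defines severe hypoglycaemia as Level 3, a determination "made by the investigator based on the medical need of the participant to have required assistance". It then adds a reporting duty: "If a hypoglycemic event meets the criterion of severe, the investigator must record the event as serious on the SAE paper form".

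**TEAE.** SAP 18.1.1: "If the AE started on or after the first treatment administration date will be considered as TEAEs". SAP 15.1 is wider and also takes in events that "or are reported to have worsened in severity after the first study drug treatment". Protocol 9.4.5 has the same wider definition. The SAP 18.1.1 list itself uses the wider idea for exposure-adjusted incidence, whose numerator is "Number of patients with new or worsened AEs during treatment period".

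**Deaths.** SAP 18.1.1 identifies deaths only by adverse event severity equal to Death. SAP 15.1 also lists an outcome of Fatal, and SAP 10.1 lists Death as an end-of-study reason. The intensity scale in protocol 10.3.4 stops at Severe.

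**Gastrointestinal events.** For the primary analysis, SAP 18.3.1 counts nausea, vomiting and diarrhoea, and lets medical review add terms up to the final analysis. The protocol endpoint is gastrointestinal AEs without restriction. SAP section 5 declares no changes from the protocol.

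**The concern.** All four items feed the primary safety endpoint of a single-arm study that has no hypothesis and no comparator, so the counts are themselves the result.

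The severe-hypoglycaemia rule treats a one-way statement (severe implies serious) as if it held both ways. The TEAE rule gives one term two meanings within one SAP, and a programmer cannot tell from the text which governs the section 18 tables. The death and gastrointestinal rules are less serious. The data stay in the report, but a primary table can disagree with another table and nothing in the SAP warns the reader.

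**Working it through.** **Severe hypoglycaemia: logic**

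1. Protocol 8.3.5: Level 3 implies recorded as serious. The converse is not stated.
2. Protocol 10.3.2 gives other routes to seriousness, including hospitalisation, and leans towards seriousness when unsure: "When in doubt as to whether hospitalization occurred or was necessary, the AE should be considered serious". Protocol 10.3.4 keeps severity and seriousness apart as concepts.
3. A Level 1 or Level 2 event with a precautionary admission is therefore serious but not Level 3. SAP 18.1.1 counts it as severe.
4. The hypoglycaemia question is put per subject and no record link is stated. Read literally, an unrelated SAE in a subject with any hypoglycaemia could also be counted. The word *corresponding* may mean event by event, so this second route is possible rather than certain.
5. The error is over-counting. No severe event is missed if sites follow 8.3.5 and the serious flag is also set on the adverse event eCRF. That second condition matters, because 8.3.5 names the paper SAE form and the SAP reads the eCRF.

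**Severe hypoglycaemia: scale**

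The plan's own numbers (protocol 9.6) reproduce: 250 × (1 − 0.20) = 200 starting treatment, and 200 × (1 − 0.20) = 160 at the end. The FAS size is not given; I take 160 to 200 as an assumed range. Exact (Clopper-Pearson) 95% intervals, if the true count is 0 and x patients are wrongly counted:

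| x | n = 160 | n = 200 |
|---|---|---|
| 0 | 0% (0 to 2.28) | 0% (0 to 1.83) |
| 1 | 0.62% (0.02 to 3.43) | 0.5% (0.01 to 2.75) |
| 2 | 1.25% (0.15 to 4.44) | 1.0% (0.12 to 3.57) |
| 3 | 1.88% (0.39 to 5.38) | 1.5% (0.31 to 4.32) |

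For the per-subject reading only, let h be the share of patients with any hypoglycaemia and s the share with an SAE, independent of each other. Expected false counts are n·h·s, and the chance of at least one is 1 − (1 − h·s)^n. The values of h and s are assumptions.

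- n = 160, h = 5%, s = 1%: 0.08 patients; 7.7%.
- n = 200, h = 10%, s = 3%: 0.6 patients; 45%.
- n = 200, h = 20%, s = 5%: 2.0 patients; 87%.

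The range is wide because the documents give neither rate.

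**TEAE**

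AEs are collected from consent, and a 2-week lead-in precedes the first dose, so pre-dose AEs will exist. The two definitions differ only for a pre-dose AE that worsens on treatment and keeps its start date. The start-date rule does agree with the incidence formula in protocol 9.4.2, which counts new AEs. The conflict is therefore confined to TEAE counts, TEAE rates and time to first TEAE.

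Assume 5% to 10% of patients have a pre-dose AE and 10% to 20% of those worsen:

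- 200 × 0.05 × 0.10 = 1 patient (0.5%)
- 200 × 0.10 × 0.20 = 4 patients (2.0%)

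These are upper bounds. A patient with another TEAE still counts, as does one whose worsening is entered as a new record.

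**Deaths**

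A fatal event graded Severe, with outcome Fatal, is missed by the 18.1.1 rule, and one such case is the difference between 0 and 1 death. Separately, SAP 18.1.2 uses the FAS and PP sets where protocol 9.4.2 uses the safety population. The FAS requires an HbA1c after treatment, first scheduled at Week 12, which is after 84 of 168 treatment days. A patient who dies before any such measurement is outside the 18.1.2 death count however death is derived.

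**Gastrointestinal events**

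The 18.3 figure falls short by at most the share of patients whose only gastrointestinal events are other terms. If that share is 1%, 5% or 10% (assumed), the shortfall is at most 2, 10 or 20 of 200, or about 2, 8 or 16 of 160.

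**The case against.** The best counter-argument is that little is lost.

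- SAP 15.2.1 already tabulates TEAEs, SAEs and AEs leading to death on the safety and PP sets, and the wider SAP 15.1 definition governs there.
- Hypoglycaemia events are listed individually (SAP 18.1.2). A natural reading of the severe rule is event by event, which leaves only serious hypoglycaemia short of Level 3, likely to be rare.
- The TEAE gap needs a lead-in AE that worsens under one record. Exacerbation of a pre-existing condition is an AE in its own right (protocol 10.3.1) and would normally carry an on-treatment start date.
- A fatal outcome appears in several fields, so a mismatch would be visible.
- All gastrointestinal terms appear in SAP 18.1.2 and 18.2.2, and protocol 9.4.2 itself uses the three terms for the severity plot and Cox models.
- The eCRF is not shown and may hold a severity or assistance field.

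Most of this stands as a limit on size. It does not repair the section 18 derivations, which are the ones labelled primary. A correct table in section 15 beside a differently derived table in section 18 is the disagreement at issue. Even on the event-by-event reading, serious does not imply Level 3. The figures from assumed rates show scale only, and the per-subject range should carry little weight. Nor should the rest of the 18.1.1 list be taken as cleared: its formula for hypoglycaemic events per patient-year counts patients rather than events and has no exposure term.

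**Conclusion.** The concern holds. Two rules in SAP 18.1.1 are wrong as written: severe hypoglycaemia can include events that are not Level 3, and the TEAE derivation omits worsened events that SAP 15.1 and protocol 9.4.5 include. The death rule and the SAP 18.3.1 gastrointestinal rule are lesser mismatches, and their consequence is tables that can disagree.

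The size is not computable, because the documents give no rate for serious hypoglycaemia short of Level 3, for worsening lead-in AEs, or for fatal events graded other than Death. At 200 patients each misclassified patient moves a proportion by 0.5 points, which matters most for severe hypoglycaemia, where the true count may be zero. This should be fixed before database lock, since a correction afterwards would be a post hoc choice.

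**What to change.** - **SAP 18.1.1, severe hypoglycaemia:** classify each event by the investigator's Level 3 determination in protocol 8.3.5. If no such field exists, use a medical review before lock of serious AEs that are themselves the hypoglycaemic event, each linked to its hypoglycaemia record.
- **SAP 18.1.1, TEAE:** replace the start-date rule with the SAP 15.1 definition, and state how worsening of a pre-dose AE is recorded.
- **SAP 18.1.1 and 18.1.2, deaths:** count a death if the outcome is Fatal, the severity is Death or the end-of-study reason is Death. Reconcile the three fields before lock, and report on the safety analysis set as protocol 9.4.2 states.
- **SAP 18.3.1:** before lock, set the primary definition to all terms in the gastrointestinal disorders SOC, keeping the three terms for the prevalence plot and Cox models. Otherwise, declare the narrowing in SAP section 5.

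The cost is SAP wording and minor reprogramming. The outcome and end-of-study fields are already listed in the SAP. The documents show no event-level assistance field, so allow for a short review of serious hypoglycaemia records, which should be few.

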4.2 Schedule of events

Refer to the protocol section 1.3 for the schedule of activities.

5. Changes/deviations from the planned analysis

The statistical analysis/methods as described in the protocol were adopted. There are no changes to the planned analyses. Any deviation from original statistical analysis plan will be described and justified in the final clinical study report.

6. Analysis populations

Agreement and authorization of participants included/excluded from each analysis population will be reached prior to final database hard lock. Sponsor will review/supply a list of all participants to be excluded from the relevant analysis populations, including the reason(s) for exclusion from the analysis populations.

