7.3 Stratifications

In general, the treatment will be presented as overall strata (i.e., Dulaglutide treatment group). However if more than 20% of the subjects undergo dose modification/downgrade or receive only 0.75 mg dose during the trial, then separate strata will be presented apart from overall: subjects with 1.5 mg only, subjects with any dose modification (at least one dose of 1.5 mg and at least 1 dose of 0.75 mg) and subjects with 0.75 mg only if they constitute more than 20% of the enrolled population. If 0.75 mg only group constitutes less than or equal to 20% of enrolled population then it can be clubbed together with the dose modified group.

Note: The dose modification may not be applicable for those who start on 0.75 mg and upgrade to 1.5 mg.

Subgroup analysis will be done on the primary, secondary, and exploratory data based on the below stratification:

- age (<65 year and \geq 65 year)
- HbA1c (<8.5 and \geq 8.5)
- Sex (Female and male)
- BMI category (<27 kg/m²) and \geq 27 kg/m²)

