8.2 Missing data

For the actual value and change from baseline, a descriptive analysis using LOCF will be performed, using the baseline or 12-week value, if the 24-week value is missing or occurred after use of rescue medication. While performing the mixed modelling with repeated measures (MMRM) Missing data will be assumed missing at random and will be accommodated by the MMRM.

If convergence is not met in the MMRM, the change in HbA1c level from baseline to Week 24 will be analysed using the general linear model and The LOCF method of missing value imputation will be used.

If none of the models converge then an analysis of covariance using LOCF imputation with similar terms as in the MMRM (except no terms that include visit) will be used in its place for body weight, fasting blood glucose, systolic blood pressure, diastolic blood pressure and pulse rate.

9. Output presentations

The templates provided in the separate output templates document describe the format and content for presentation of tables, listings, and figures (TLFs).

Summary statistics will be provided for the observed value and change from baseline will be summarized.

Unless otherwise specified, testing effect of dulaglutide on change from baseline will be conducted at a 2-sided alpha level of 0.05, and CIs will be calculated at 95%, 2-sided.

For continuous measures, summary statistics will include number of patients, mean, SD, median, minimum, maximum, and interquartile ranges for both the actual and the change from baseline measurements. Number of missing values will be specified along with this information.

For categorical measures, summary statistics will include sample size, frequency, and percentages. Number of missing values will be specified along with this information.

10. Participant disposition and withdrawal**10.1 Variables and derivations**

The trial classifications are defined as follows:

- Screening failure:

Individuals who do not meet the criteria for participation in this study (screen failure) may be rescreened after 4 weeks from the date of screen failure after discussion with the medical monitor.

- Completed trial:

A participant is considered to have completed the study if the participant has completed all periods of the study including the last visit.

- Lost to follow-up:

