12.1 Variables and derivations

The date of first treatment administration will be derived as the first date of dosing from the exposure eCRF page.

The following parameters will be presented for the exposure summary:

- Number of subjects received first dose
- Number of subjects received weekly doses by each visit
- *Duration of exposure (days) =*
(Date of last treatment administration - Date of first treatment administration) + 1

Compliance will be calculated as follows:

- Compliance with the study treatment (%) = (Actual Dose/ Planned Dose)*100

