18.1.2 Analyses

Population: FAS and PP

Stratification: Table: Add the strata as needed in case subjects with dose modification exceeding 20% based on enrolled population as per section 7.3:

- a. Subjects on 1.5 mg only
- b. Subjects on 0.75 mg only
- c. Subjects with any dose modification*

* Subjects who have received at least one dose of 1.5 mg and at least one dose of 0.75 mg

Listing: by subject and events

Statistics: The incidence of AEs (including deaths, SAEs, TEAEs, hypoglycemia, including severe hypoglycemia and GI disorders) will be summarised as frequency and percentages.

The listings will be presented for the hypoglycaemia events.

The incidence of AE (death, SAE, and TEAE) will be summarized. The rate per year (i.e., number of deaths, SAE, and TEAEs per subject per year over the study period) will be assessed using a negative binomial model with the log of the study treatment exposure time as an offset variable and the model will be performed as per details mentioned below.

The incidence of hypoglycemic AEs will be summarized. The number of hypoglycemic events per subject over the study period will be analysed as continuous variables and will be summarized as (n, mean, standard deviation, standard error, median, minimum, maximum).

The rate per year of hypoglycemic events, that is, the number of hypoglycemic events per patient-year (365.25 days) will be assessed using a negative binomial model, with baseline HbA1c and baseline insulin usage as covariates and the log of the study treatment exposure time as an offset variable.

The Negative Binomial Model i.e., the generalized linear model will be used with baseline HbA1c and baseline insulin usage and the log of the study treatment exposure time as offset variable.

The incidence rate, least square mean and corresponding 95% confidence interval will be provided for table.

Also, in case we have more than 20% data missing in any of the covariate, we will repeat the analysis after omitting the impacted covariate.

In case of multiple doses of insulin uptake per day, a sum of insulin per day will be used as the baseline insulin covariate. Regimen for subjects with more than 1 regimen type per day will be reviewed by

medical team. Insulin Dose level for subjects not on insulin will be considered as 0 and the corresponding regimen as 'Non'.

In case convergence is not met with the above variables, only baseline HbA1c and baseline insulin usage(Yes/No) will be considered.

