Exposure-adjusted AE incidence will be presented by the severity and preferred term for the primary analysis.

Additionally, all the analysis will be repeated for the below mentioned subgroups:

- age (<65 year and \geq 65 year)
- HbA1c (<8.5 and \geq 8.5)
- Sex (Female and male)
- BMI category (<27 kg/m²) and \geq 27 kg/m²)

18.2 Proportion of patients reporting AEs and SAEs between baseline and Week 24

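### SAP 18.1.1 defines the hypoglycemic event rate as affected patients divided by 365.25, which counts the wrong unit and contains no exposure time

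*SAP*

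**What the plan says.** Hypoglycemia, including severe hypoglycemia, is named within the first primary endpoint (protocol section 3, SAP 3.1). The list of derivations in SAP 18.1.1 includes: "Number of hypoglycemic events per patient-year (365.25 days)= Number of patients with hypoglycemic events /365.25".

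The next item in that list is a different quantity: "Exposure Adjusted AE Incidence= Number of patients with new or worsened AEs during treatment period / (Patient-year exposure/365.25", closed by a bracket. The item after it says that this exposure is counted in days.

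Protocol 9.4.2 and SAP 18.1.2 both describe the yearly rate of hypoglycemic events as events per patient-year, estimated with a negative binomial model. Baseline HbA1c and baseline insulin usage enter that model "as covariates and the log of the study treatment exposure time as an offset variable". SAP 18.1.2 also summarises the number of hypoglycemic events per subject as a continuous variable, so it expects some patients to have more than one.

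SAP 18.1.2 then adds: "Additionally, all the analysis will be repeated for the below mentioned subgroups". Under SAP 7.3, dose strata are shown as well "if more than 20% of the subjects undergo dose modification/downgrade or receive only 0.75 mg dose during the trial".

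**The concern.** The same name, events per patient-year, is attached to two different things: a headcount divided by a constant in 18.1.1, and an exposure-based event rate in 18.1.2 and the protocol. Section 18.1.1 is where a programmer looks for formulas, and this is the only explicit formula there for the named quantity. A crude rate built from it would understate hypoglycemia and disagree with the model estimate. Because the line grows with the number of patients, it would also mix group size with risk when subgroups are set side by side.

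**Working it through.** **Inputs**

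- Protocol 9.6: 250 screened with 20% screen failure gives 250 × 0.80 = 200 starting treatment. With 20% dropout, 200 × 0.80 = 160 finish. Both planning figures reproduce.
- Treatment period: 24 weeks = 168 days.
- SAP 12.1 measures duration of exposure as "Date of last treatment administration - Date of first treatment administration) + 1". For 24 weekly doses that is 23 × 7 + 1 = 162 days. The SAP does not say whether the model offset uses this definition, so both lengths are shown.
- Numbers of affected patients and of events are not in the documents. Those used below are assumptions.

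**Formulas**

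- Line as written: affected patients / 365.25.
- Crude event rate: events / (total exposure days / 365.25).
- Ratio of the second to the first: (events per affected patient) × 365.25 / patient-years.

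The adjacent formula in 18.1.1 helps by contrast: there 365.25 only converts days to years and is not a denominator on its own.

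**Patient-years and shortfall at one event per affected patient**

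| When the 40 dropouts leave | 162 days | Fold too low | 168 days | Fold too low |
|---|---|---|---|---|
| At the end | 200×162/365.25 = 88.7 | 4.12 | 200×168/365.25 = 92.0 | 3.97 |
| Midway | (160×162+40×81)/365.25 = 79.8 | 4.57 | (160×168+40×84)/365.25 = 82.8 | 4.41 |
| Day 1 (extreme) | (160×162+40×1)/365.25 = 71.1 | 5.14 | (160×168+40×1)/365.25 = 73.7 | 4.96 |

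The range is 4.0- to 5.1-fold. SAP 18.1.2 names the FAS and per-protocol sets. The FAS needs a post-treatment HbA1c, first scheduled at Week 12, so very early leavers would normally fall outside it. Using the 160 completers alone gives 160×162/365.25 = 71.0 patient-years and 365.25/71.0 = 5.1-fold, so the range hardly moves.

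**Repeat events (assumed: 20 patients, 40 events)**

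- Line: 20/365.25 = 0.055.
- Crude rate: 40/92.0 = 0.43 to 40/71.1 = 0.56 per patient-year.
- Shortfall: 7.9- to 10.3-fold.

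**Group size (assumed: groups of 150 and 50, full follow-up, 162 days, one event per affected patient)**

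Patient-years are 150×162/365.25 = 66.53 and 50×162/365.25 = 22.18.

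- Equal 10% risk: the line gives 15/365.25 = 0.041 and 5/365.25 = 0.014, an apparent 3-fold gap. The crude rates are equal, 15/66.53 = 5/22.18 = 0.225.
- Risk doubled to 20% in the smaller group: the line gives 10/365.25 = 0.027 against 0.041, so the smaller group ranks lower. Its crude rate is 10/22.18 = 0.451 against 0.225.

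**The case against.** The strongest reply is that no planned output is shown to use this line. Protocol 9.4.2 and SAP 18.1.2 both assign the yearly rate to the negative binomial model, and the non-convergence rule in 18.1.2 simplifies the covariates without leaving the model. The incidence rate promised for the table directly follows the model text, so it reads most naturally as model output. This stands, and it makes the harm conditional.

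A reader might infer that the reported hypoglycemia rate will be wrong. The documents do not support that. The model is specified correctly, and no passage sends the 18.1.1 line to a table. SAP section 9 says "The templates provided in the separate output templates document describe the format and content" of the tables, and that document is not available here, so the point cannot be settled either way.

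A reader might also infer an undeclared departure from the protocol, since SAP section 5 states "There are no changes to the planned analyses". That does not follow. The analysis planned in protocol 9.4.2 is the model, and SAP 18.1.2 keeps it. A stray derivation line does not change a planned analysis.

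Nor does the adjacent formula contradict the line. It defines another quantity, and its numerator is also patients. It shows only what 365.25 is for.

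The event counts, the 150/50 split and the risks are invented for illustration, and dose strata appear only if the SAP 7.3 trigger is met. The subgroup repeats, however, are planned without a trigger. None of this rescues the formula itself.

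**Conclusion.** The line is wrong as written: it counts patients where its label says events, and it has no person-time. It contradicts protocol 9.4.2 and SAP 18.1.2. That part needs no assumption.

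The consequence is conditional. The model rate is sound if it is fitted to event counts with the stated offset. Only a crude rate programmed from 18.1.1 would carry the error. It would then be about 4- to 5-fold too low at one event per affected patient, given 200 starters, 20% dropout and 162 or 168 days of exposure. The shortfall grows in proportion to the number of events per affected patient, and the figure would not be comparable between groups of different size.

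It should be corrected because it is a false definition under a primary endpoint and the correction is cheap. No reported result has been shown to be affected.

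**What to change.** Replace the line in SAP 18.1.1 with: total number of hypoglycemic events / (total exposure days / 365.25). Use the same event-counting window and the same exposure time as the negative binomial model in 18.1.2, overall and in each subgroup or dose stratum presented. Adding exposure alone is not enough, because patients / (exposure days / 365.25) is still not an event rate.

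Do not tie the window to the SAP 12.1 duration. For 24 weekly doses it closes on day 162, so events on days 163 to 168, in the last dosing week, would be lost. The crude count could then disagree with the 18.1.2 counts, which run over the study period.

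If no crude rate is wanted, delete the line and refer to the 18.1.2 model.

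Cost: one formula in the SAP and, if a crude rate is tabulated, its program. No protocol change.
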